To estimate the treatment effects for palbociclib plus letrozole using propensity score matching across imputed datasets we will apply the “within” approach using the “MatchThem” R package.^{30,31} That is, propensity score matching and the estimation of the treatment effect are performed in each imputed dataset separately and resulting treatment effect estimates are combined using Rubin’s rule. In this study, this will be implemented by matching eligible patients on their propensity to initiate palbociclib plus letrozole using a 1:1 nearest neighbor matching algorithm without replacement and a caliper of 1% of the standard deviation of the propensity score. The resulting covariates balance will be assessed by computing and visualizing ASMDs before and after matching across datasets. As compared to a single dataset matching approach, this can lead to a range of ASMDs per covariate due to random variation across imputed datasets for which an example (using simulated data) is illustrated in Figure 3. If sufficient balance can be established, a Cox proportional hazards regression model will be fit to estimate the marginal average treatment effect in the matched population. Since in most databases there are more palbociclib-plus-letrazole patients than patients in the control arm, the estimand will rather correspond to the ATC than the ATT. Confidence intervals will be estimated using cluster-robust standard errors.³² As a secondary endpoint, we will additionally estimate the median OS survival time difference between the two exposure groups using the Kaplan-Meier method. It should be noted that due to administrative and de-identification purposes, the date of death is often only available at the month- or year-granularity level, in which case the date of death will be imputed to the 15th of a month or July 2nd of a year, respectively (depending on the database). In rare cases, this can lead to negative/implausible follow-up times if the date of death is very close to the index date. These patients will be excluded from the analysis.

The final hazard ratio and median OS survival time difference estimates for each database will then be combined using Rubin’s rule.^{29,33} To arrive at a single estimate across databases, the final estimates will be summarized through a meta-analytic fixed effects model.³⁴ A summary of the analytic approach is summarized in Table 7 and an example workflow with simulated data and annotated code can be found [here](#).

A. Primary analysis

Table 7. Primary, secondary, and subgroup analysis specification

Hypothesis:	Initiation of palbociclib plus letrozole decreases the hazard of all-cause mortality as compared to initiation of letrozole alone
Exposure contrast:	Initiation of palbociclib plus letrozole vs letrozole alone
Primary outcome:	Time to all-cause mortality (OS)
Secondary outcome:	Time-to-next-treatment (TTNT) defined as a composite outcome of all-cause mortality or adding or switching to a next-line treatment. ^{35,36}
Databases used:	EDB1 and EDB3 (primary analysis), EDB4 (sensitivity analysis)
Time period:	From 2015 (approval year for palbociclib) - 2022 (publication of final OS outcome results for competitor ribociclib) ⁷
Analytic software:	R 4.3.2. Version control of code and R packages will be established through git and Posit package manager, respectively. All packages are frozen to their most recent version as of April 25, 2024.
Model(s): (provide details or code)	See example code here . The annotated code for the trial emulation will be hosted at https://drugapi.gitlab-pages.partners.org/encore/paloma2-nct-01740427/ (access only through MGB network for authorized personnel)
Confounding adjustment method	Name method and provide relevant details, e.g. bivariate, multivariable, propensity score matching (specify matching algorithm ratio and caliper), propensity score weighting (specify weight formula, trimming, truncation), propensity score stratification (specify strata definition), other.
	1:1 propensity score nearest neighbor matching without replacement and a caliper of 1% of propensity score standard deviation
Missing data methods	Name method and provide relevant details, e.g. missing indicators, complete case, last value carried forward, multiple imputation (specify model/variables), other.
	Multiple imputation by chained equations using a random forest imputation model across all covariate types. The number of imputed datasets will be determined by the average proportion of missing values across all partially observed covariates. Imputation models will include all variables of the substantive model, i.e., exposure, outcome, confounders/prognostic factors and additional auxiliary covariates.
Subgroup Analyses	List all subgroups
	
In subgroup analysis, multiple imputation, propensity score matching and balance assessment will be conducted within each subgroup separately. The treatment effect will be estimated for each stratum separately (stratum-specific effects).
 
 1. Age (<65, ≥65) 2. Region (North America, Europe, Asia/Pacific) 3. ECOG (0, 1) 4. Disease-free interval (De-novo metastatic, ≤12 months, >12 months) 
According to Slamon et al,⁶ the subgroup analyses are considered exploratory in nature and performed with no formal statistical testing.

Table 8. Sensitivity analyses – rationale, strengths and limitations.

	What is being varied? How?	Why? (What do you expect to learn?)	Strengths of the sensitivity analysis compared to the primary	Limitations of the sensitivity analysis compared to the primary
Sensitivity #1	Caliper matching on ROPRO prognostic score instead of propensity score	Matching patients on validated prognostic score may be more beneficial to control for (unmeasured) confounding	Matches patients on validated prognostic score that incorporates weights of key prognostic factors	Limited experience on how to optimally use prognostic scores and should be seen as an experimental sensitivity analysis
Sensitivity #2	Average treatment effect in the overlap population (ATO) weighting instead of matching	Weights that resemble the average treatment effect in the overlap population (ATO) create a clinical equipoise population which is comparable to an RCT	ATO weighting usually results in excellent balance and clinical equipoise	Estimates the average treatment effect among the overlap patients which may not be comparable to target population anymore
Sensitivity #3	SMR/ATT weighting instead of matching. Here symmetric trimming (i.e., setting all weights lower/higher than that at a given quantile to the weight at the quantile) of extreme weights may be considered with the quantiles chosen based on weight distribution and resulting balancing performance.	SMR weighting retains all patients and resembles the same estimand as matching	ATT weighting retains all patients	Patients with extreme weights after trimming may bias the analysis
Sensitivity #4	Censoring date is changed to 3 months before data cut-off date	For all databases, information on mortality comes from different data sources which are updated asynchronously. To account for the potential lag of updated mortality information (ghost-time bias ³⁷), the censoring for patients without mortality event in the whole patient identification period will be moved to last sign of patients being alive/visit or 3 months before data cut-off date, whichever occurred earlier. ³⁸	Approach implements a more conservative censoring rule	Approach addresses ghost-time bias by censoring patients without a recorded death event earlier
Sensitivity #5	Delta imputation models for MNAR (tipping point analysis)	Primary multiple imputation analysis assumes MAR which	Estimates impact of deviations from MAR assumption on final	Delta parameters must be assumed and results are complex to interpret in

		may not hold for every covariate	treatment effect estimates for key covariates	multivariate missingness settings; just most important covariates or those with highest suspicion of being MNAR will be evaluated
Sensitivity #6	Re-weighting of strong risk factors and/or treatment effect modifiers distribution to match that of PALOMA-2	In the presence of effect modification, treatment effect estimates may be different if the distribution of strong risk factors/effect modifiers is different in the emulated cohort versus the trial cohort	Re-weighting adjusts for differences in distributions of key risk factors and/or treatment effect modifiers (see subgroup analysis in Table 7)	Re-weighting risk factors/potential effect modifiers to match the PALOMA-2 trial and simultaneously balancing them across treatment groups may be challenging due to differences in measurement
Sensitivity #7	Including patients who have had at least 1 visit 90 days prior to treatment initiation	EHR are often lacking data continuity, and this analysis uses the requirement of 1 visit as a proxy for continuous observation periods	Considers aspect of data continuity	There may be patients who are put on treatment immediately in which case they are falsely excluded
Sensitivity #8	Using all available calendar time	This analysis explores potential confounding related to calendar time, evolving clinical practice patterns, and access to therapies.	Aims to assess the extent of confounding introduced by changes in time, treatment practices, and access to therapies.	We expect the results to be more confounded due to calendar time.
Sensitivity #9	Missingness is handled by restricting to patients with complete observations on a subset of the most important confounders (“complete cases”).	Instead of imputing data, this sensitivity analysis restricts the analysis cohort to patients with complete observations on key confounders	Data will not be imputed and missingness is assumed to be missing completely at random	The restriction to complete cases will significantly decrease sample size. To limit the attrition of patients with partially observed covariates, it won’t be possible to use all covariates used in the main analysis propensity score model, but only consider key covariates with overall low proportions of missingness (age, sex, etc.)
Sensitivity #10	Exclusion of patients with >1 year between metastasis diagnosis and index date	This sensitivity analysis varies the inclusion criteria by excluding patients whose index date (treatment start) is >1 year after their metastatic diagnosis date which is	Helps ensure that treatment reflects initial first-line treatment of metastatic disease, not late-line therapy.	Exclusion of further patients results in a smaller cohort size which may reduce statistical power.

		clinically unrealistic or implausible for a first-line treatment		
Sensitivity #11	Addition of EDB4	EDB4 is not considered in primary analyses for reasons given in section 6.1.1.	Increased sample size and potentially broader coverage of general US cancer population	See limitations listed in section 6.1.1 regarding potential immortal time and selection bias due to left truncation .
Sensitivity #12	Descriptive analysis of switching/crossover patterns in the trial and its emulation	This sensitivity analysis assesses crossover patterns comparatively in the trial and its emulation	Help to understand the potential concordance/discordance of treatment effects between the trial and its emulation	Analysis is on the description level, which may limit conclusions

7. Limitation of the methods

- Missingness in prognostic factors is a major challenge which is addressed in this emulation by multiple imputation using a non-parametric imputation algorithm. Multiple imputation usually assumes that missingness can be explained by observed characteristics, which may be empirically evaluated using principled missingness diagnostics, but the true underlying missingness mechanisms are usually unknown. Nevertheless, multiple imputation makes use of additional information (auxiliary covariates) which can render the underlying missingness assumptions more plausible. In addition, assumptions for alternative missing data approaches like complete case analysis or the “missing indicator approach” come with even stronger assumptions and additionally have the limitation of significantly reduced sample sizes, especially when comprehensively adjusting for known confounders and prognostic factors.
- Data continuity is a major challenge in EHR databases since “guaranteed” observable periods (such as continuous enrollment periods in administrative claims data) do not exist which may lead to measurement error in key covariates and exposure misclassification. Sensitivity analysis #7 tries to address this requiring patients to have had at least one visit before the index date which increases the likelihood that a patients was not only diagnosed at the respective center but is also regularly seen.

8. Protection of human subjects

This study has been approved by the Brigham and Women’s Hospital Institutional Review Board.

9. References

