6.6. Setting

6.6.1. Context and rationale for definition of time 0 (and other primary time anchors) for entry to the study population

Time 0 in this database study is defined as the date a patient initiated palbociclib plus letrozole (exposure) or letrozole alone (comparator) as part of their 1L systemic antineoplastic treatment for advanced/metastatic adenocarcinoma of the breast. This aims to emulate the date of randomization and cohort entry in the RCT (the time from randomization to first dose is not reported in the [clinicaltrials.gov study report](https://clinicaltrials.gov/study/NCT02420417) or the trial articles).

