6.6.5. Context and rationale for outcome(s) of interest

The primary outcome for the database study was defined to emulate the primary outcome for the trial, time from index to death due to any reason (OS).

Operational definitions:

- **EDB1:** Time in [days, months and years] from index date to death due to any reason. The date of death is de-identified to month-level granularity or (rarely) to year-level granularity and the date of death is therefore imputed to the 15th of a month or mid-year/July 2 of the year of death, respectively. In If there is no indication that a patient died during the study period, the patient is censored. The censoring date is defined as the last visit or treatment encounter or data cut-off date, whichever occurred earlier. The OS endpoint is operationalized using a parameterized R function *edb1_get_os()* and more details can be found in the attached pdf documentation.
- **EDB3:** Time in [days, months and years] from index date to death due to any reason. The date of death is de-identified to month-level granularity and the day of death is therefore imputed to the 15th of a month. Patients without evidence of death are censored at the earlier of the last recorded activity date or the data cut-off date. Activity dates are defined as documented in Table 4. Death dates are compiled from Electronic Medical Records (EMR), manual curation, and third-party death data, linked via de-identified tokens generated from hashed personally identifiable information (PII). Sources of death dates are prioritized as follows: (1) manual curation, (2) EMR, and (3) third-party sources. For privacy reasons, the final reported death date is shifted to the nearest Sunday within four days of the actual date. Manually curated death dates follow a prioritization hierarchy of source documentation: death certificate first, followed by scanned obituaries or death announcements, and lastly exact dates reported by providers without other supporting documentation. The OS endpoint calculation uses a parameterized R function (*edb3_get_os()*), with detailed documentation provided in the attached PDF.

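### Dropping patients whose imputed death date precedes the index date selects on the primary outcome; the expected effect is small and its direction is unknown

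*Combined protocol and SAP*

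**What the plan says.** Section 6.7.1 covers death dates available only to the month or the year, "in which case the date of death will be imputed to the 15th of a month or July 2nd of a year, respectively". It names the side effect itself: "In rare cases, this can lead to negative/implausible follow-up times if the date of death is very close to the index date". The handling is one sentence: "These patients will be excluded from the analysis".

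Section 6.6.5 gives the granularity by database. For EDB1: "The date of death is de-identified to month-level granularity or (rarely) to year-level granularity". For EDB3: "The date of death is de-identified to month-level granularity and the day of death is therefore imputed to the 15th of a month". The same EDB3 paragraph, and the data-linkage row of Table 3, also describe a different rule: "For privacy reasons, the final reported death date is shifted to the nearest Sunday within four days of the actual date".

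Four other parts of the plan bear on this:

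- OS is the primary outcome (Table 7). Section 6.6.6 limits the study to ITT analyses, and Table 2 likens the causal contrast to ITT.
- Section 6.6.1 places time 0 at treatment initiation. Section 6.6.4 starts follow-up once the exposure assessment window has closed, for all three databases. The window rules are proprietary (Figure 1, note a), so its length is not given.
- The plan gives no count of patients expected to be dropped and no split by arm. It does not say whether they leave before or after imputation and matching.
- None of the 12 sensitivity analyses in section 6.7.1 retains them (#4 changes only censoring), and section 7 does not list the rule as a limitation.

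**The concern.** A patient without a recorded death has no imputed death date, so the rule cannot touch survivors. A patient who starts on the 20th and dies on the 28th is assigned the 15th, gets minus 5 days of follow-up and leaves the analysis. The plan attributes that negative time to its own imputation, not to a faulty record. An ITT analysis of a trial would count the death.

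The rule also sits badly with section 6.1.1, which takes EDB4 out of the primary analysis because inclusion there depended on surviving to a date. The exclusion brings a small version of the same dependence into EDB1 and EDB3. It affects the OS hazard ratio and the median OS difference, and also TTNT, because death is a component of that composite. The study exists to test agreement with a near-null trial result, so selection that can be avoided is worth avoiding even when it is small.

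**Working it through.** **Inputs.** From the documents: trial median OS 53.9 and 51.2 months and OS HR 0.96 (section 4); matched sets of 1812 with 1021 events (EDB1) and 610 with 331 events (EDB3), and design HR 0.92 (section 10.3). Assumed: constant hazard, index days spread evenly over the month or year, and a mean month of 30.44 days. The share of year-level dates and any raised early hazard are also assumptions, shown as ranges.

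**1. The plan's own figures.** The plan states no figure for this exclusion. Its power figures reproduce, which supports the event counts used below. Power = Φ(|ln 0.92| × √(events × 0.25) − 1.96), two-sided 5%:
- EDB1: Φ(0.0834 × 15.98 − 1.96) = 0.265 (stated 0.27).
- EDB3: Φ(0.0834 × 9.10 − 1.96) = 0.115 (stated 0.11).

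**2. Who can be dropped.**
- Month-level date: index after the 15th and death in the same month. The latest case is index on the 16th and death on the 31st, which is 15 days.
- Year-level date: index after July 2 and death in the same year. The latest case is July 3 to December 31, which is 181 days.

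**3. Share of same-month deaths dropped.** (15.4/30.4)² = 26%.

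**4. Share of patients dropped, month-level dates.** Approximately λ × (30.44 − 15)² / (2 × 30.44) = λ × 3.92 days, with daily hazard λ = ln 2 / (median × 30.44).
- Median 51.2: λ = 0.000445, share 0.17%.
- Median 53.9: λ = 0.000423, share 0.17%.
- This is about 3 of 1812 in EDB1 and 1 of 610 in EDB3.
- At 2 to 3 times the hazard soon after index (assumed): 0.33% to 0.52%, or about 6 to 9 in EDB1 and 2 to 3 in EDB3.

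**5. Year-level dates in EDB1.** Among patients with year-level dates the dropped share is about 1.9% to 2.0% at the base hazard. Let f be the fraction of EDB1 patients with such dates, and m and y the month-level and year-level dropped shares. The expected loss is 1812 × [(1 − f)m + f·y]. For f from 1% to 10% this is about 3 to 6 patients. At three times the hazard with f = 10% it is about 19.

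**6. Effect on the HR.** Take equal person-time and split events so that the ratio starts at 0.96. EDB1 then has 520.9 letrozole and 500.1 palbociclib deaths; EDB3 has 168.9 and 162.1.

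| Deaths lost | HR |
|---|---|
| 1 from each arm, either database | 0.960 |
| EDB1, 3 from letrozole only | 500.1/517.9 = 0.966 |
| EDB1, 10 from letrozole only | 500.1/510.9 = 0.979 |
| EDB3, 1 from letrozole only | 162.1/167.9 = 0.966 |
| EDB3, 3 from letrozole only | 162.1/165.9 = 0.977 |

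Losses confined to the palbociclib arm would move the HR the other way.

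**7. Against sampling error.** In EDB1 the SE of the log HR is about 2/√1021 = 0.063. A move from 0.960 to 0.966 is ln(0.966/0.960) = 0.006, about 0.1 SE.

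**The case against.** The strongest objection concerns the start of follow-up. With month-level dates, a dropped death lies within about 15 days of index. If section 6.6.4 governs and the undisclosed window is longer than that, these patients were never at risk in the analysis. Counting them one day after index would then place deaths inside the window. It could also load the control arm, because a patient who dies before palbociclib is added would be classed as letrozole alone. This stands. The remedy cannot be written until sections 6.6.1 and 6.6.4 agree.

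Two further points are fair. The plan discloses the rule and calls the cases rare, and the arithmetic supports rare. The 2 to 3 times early hazard has no source in the documents, and the cohort is limited to ECOG 0 or 1 without CNS metastases.

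A reader might infer that every excluded patient is a genuine eligible initiator. The documents do not support that. Table 5 reports negative intervals from imprecise line-of-therapy dates, and EDB3 deaths are linked by hashed tokens, so some negative times may be date or linkage errors. Coarse index dates would also weaken the even-spread assumption. Nor would a Sunday-shifted date in EDB3 end the problem: a shift of up to four days can still put death before index.

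None of this justifies the exclusion where the recorded death period is compatible with survival past the start of follow-up.

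**Conclusion.** The rule selects on the primary outcome, departs from the plan's ITT-like contrast, and is covered by no sensitivity analysis or stated limitation. It should be changed, but as a small correction. The expected loss is about 0.17% of patients, with an HR shift of about 0 to 1%. The shift reaches about 2% if losses are larger and fall in one arm (10 deaths in EDB1 or 3 in EDB3). The case of 19 deaths in step 5, all in one arm, would go further (500.1/501.9 = 0.996). It needs a tripled hazard, 10% year-level dates that the plan calls rare, and complete one-sidedness.

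It is tempting to conclude that the rule hides letrozole deaths because frailer patients are channelled to letrozole alone. The documents show no early deaths by arm, and the plan matches on ECOG, laboratory values and number of metastatic sites. Only deaths can be removed, but the direction of any HR bias is unknown.

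These sizes rest on a constant hazard, evenly spread index days and time running from initiation. The documents do not say whether 1812 and 610 are counts before or after the exclusion; at this size it hardly matters.

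**What to change.** 1. Use one start of follow-up throughout, reconciling sections 6.6.1 and 6.6.4.
2. Where the recorded death month or year includes or follows that start, keep the patient as an event. If the imputed date is not after the start, set death to the midpoint between the start of follow-up (or last later activity) and the end of the recorded month or year, with a minimum of 1 day.
3. Exclude only where the recorded death month or year ends before the start of follow-up.
4. Report excluded and re-dated patients by arm and database, and run the plan's present exclusion as a sensitivity analysis. If follow-up starts after the window, a death in the month containing that start may have fallen inside the window. The counts and the sensitivity analysis would show how much that matters.
5. Separately, reconcile the two EDB3 death-date statements in section 6.6.5, and use the Sunday-shifted date if it is delivered.

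The cost is a revised sentence in section 6.7.1, one added sensitivity analysis, and changes to the functions that derive OS. Their documentation is not in the text, so the coding effort is unverified. No patients are lost and power is essentially unchanged. The harder part is step 1, which the plan needs in any case.
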